### *Research Design and Methodology*

In this prospective cohort study, participants referred for a sleep study by in-lab polysomnography at the Jordan University Hospital and those who preferred their study conducted at a private clinic or by at-home sleep study will be screened and physically examined for any facial discoloration which will be accordingly graded as low, moderate, or high based on severity of difference from normal skin color and texture and pictured with patients' consent and privacy maintained. In addition to a general history, participants will be asked in detail about their smoking habits, vasovagal symptoms, sleeping habits, and any specific obstructive sleep apnea symptoms. After the sleep study is performed, positive and negative results will be collected and correlated with presence of facial discolouration. Severity of OSA will be graded by apnea-hypopnea index (AHI) and recorded as mild (5 - 15 events/hour), moderate (15 - 30 events/hour), or severe (> 30 events/hour). Participants with positive results will then be followed up with at 3 weeks and 6 months to determine what treatment they were given, assessed for improvement on treatment, and be questioned regarding smoking and vasovagal symptoms again. Improvement is defined as better sleep quality and reduction of initial symptoms. Participants with negative results will also be followed up with and asked about their smoking habits and vasovagal symptoms. Correlation will then be made between the group that improved on treatment and the group that did not (whether due to ineffective treatment or not receiving treatment at all) to see if improvement reduces smoking tendency with alleviated vasovagal symptoms, and compared with participants with negative sleep study results for any change in smoking habits as well.

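### Improved and not-improved patients are compared on smoking change, and the result is read as an effect of improvement, without conditioning on baseline smoking level or OSA severity

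*Protocol*

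**What the plan says.** All of this is in the protocol, Research Design and Methodology, unless stated otherwise.

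- **Baseline.** At entry, "participants will be asked in detail about their smoking habits, vasovagal symptoms, sleeping habits, and any specific obstructive sleep apnea symptoms". No unit or quantity of smoking is named. OSA severity is graded from the AHI as mild, moderate or severe.
- **Follow-up.** Positives are seen at 3 weeks and 6 months and will "be questioned regarding smoking and vasovagal symptoms again". For the others: "Participants with negative results will also be followed up with and asked about their smoking habits and vasovagal symptoms".
- **Contrast within positives.** "Correlation will then be made between the group that improved on treatment and the group that did not". The second group pools patients whose treatment did not work with patients who had none. The stated purpose is "to see if improvement reduces smoking tendency with alleviated vasovagal symptoms".
- **Contrast with negatives.** These groups are also "compared with participants with negative sleep study results for any change in smoking habits as well".
- **Population.** Population and Sample describes purposive sampling of adults referred for a sleep study. It sets no smoking criterion, so smokers and non-smokers can both enter.

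The text names no covariate, no stratification by baseline smoking and no restriction to smokers.

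**The concern.** The protocol fixes the groups, the outcome and a causal reading, but nothing in the design balances the groups. One split is by diagnosis and the other by a response seen after baseline.

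Change in smoking depends on where a patient starts. A non-smoker cannot cut down, and a heavier smoker has more room to fall and tends to regress further towards the mean. If baseline smoking or OSA severity also bears on who improves, the improved and not-improved groups start apart, and their changes differ even if improvement does nothing to smoking.

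The direction is not known in advance. If the improved group started heavier, the artefact favours the hypothesis. If the not-improved group did, it masks a real association. Leaving out a strong baseline predictor also costs precision.

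**Working it through.** **No figure to reproduce.** The protocol states no sample size, SD, effect size, alpha or power. Every number below is an assumption chosen to show the mechanism.

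**1. Spurious difference in change.** Let d be the baseline gap in mean cigarettes/day, and rho the correlation between baseline and follow-up. Assume equal SDs, a regression line common to both groups and no group effect given baseline. Then:

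difference in mean change = -(1 - rho) x d

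The minus sign means that the heavier group appears to cut down more. With d = 5:

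| rho | (1 - rho) x 5 |
|---|---|
| 0.5 | 2.5 |
| 0.6 | 2.0 |
| 0.7 | 1.5 |
| 0.8 | 1.0 |

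At d = 0 or rho = 1 the artefact is zero.

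**2. False-positive rate.** Add an assumed SD of 10 cigarettes/day, 100 patients per group and a two-sided test at 0.05. The SD of change is 10 x sqrt(2(1 - rho)). At rho = 0.5 this is 10, the standard error of the difference is 10 x sqrt(2/100) = 1.41, and the artefact of 2.5 is 2.5/1.41 = 1.77 standard errors. The chance of rejecting with no true effect is then 42%. It is 28% at rho = 0.7 and 12% at rho = 0.9.

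A simulation of 1,000 runs per setting, with gaps of 2, 5 and 8 and rho of 0.5, 0.7 and 0.9, gave rejection rates of 4.4% to 5.5% once baseline was a covariate. That simulation used the same common regression line, so it confirms the algebra and does not test the assumption.

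**3. Precision.** Residual variance with baseline as covariate, relative to the change score:

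(1 - rho²) / (2(1 - rho)) = (1 + rho) / 2

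This is 0.75, 0.80, 0.85 and 0.90 at rho = 0.5, 0.6, 0.7 and 0.8, a reduction of 25% down to 10%.

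**4. A yes/no outcome.** If the outcome were any reduction in smoking, suppose 60% of one group and 30% of the other smoke, and 20% of smokers in each cut down. Then 0.60 x 0.20 = 12% and 0.30 x 0.20 = 6% show a reduction, a ratio of 2.0 with no effect.

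**5. The opposite case.** Suppose instead that the gap between groups is stable: each regresses towards its own mean and nothing changes. The change score is then correctly 0. The baseline-adjusted difference is d - rho x d = (1 - rho) x d, again 2.5 down to 1.0 for d = 5, and now it is the adjusted figure that is spurious. Which case applies cannot be settled from baseline and follow-up means alone.

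**The case against.** **Covariates are commonly left to the SAP.** An SAP may exist, and the protocol nowhere says that the comparison is unadjusted. This stands as a limit on confidence: a reader might infer that the final analysis will be unadjusted, and silence does not show that. What remains is that the protocol itself sets out the contrast and attaches a causal reading to it, with no provision for starting level.

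**Baseline is already used.** A reader might infer that the plan ignores baseline smoking. It does not, because change and reduction take each patient's own baseline as reference. What is absent is conditioning on it.

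**The protocol's premise does not imply a gap here.** A reader might infer that the groups must start at different smoking levels because OSA is supposed to drive smoking. At most, and only by inference, that supports a gap between positives and negatives. For improved versus not improved a gap is possible, but the text neither states nor implies one.

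**Adjustment can itself mislead.** Step 5 of the working stands for positives versus negatives: if OSA sustains a stable gap, a baseline-adjusted difference can be an artefact. The documents therefore do not support requiring a baseline covariate as the single answer in every contrast. The objection is much weaker within positives, where improvement is determined after baseline and may depend on baseline smoking and severity.

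**Adjustment does not make the contrast causal.** This also stands. The groups are formed by post-baseline response, and the comparator mixes ineffective treatment with none.

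**Conclusion.** The point holds in a limited form. Among sleep-study positives, the protocol reads a contrast of self-formed groups as an effect of improvement without conditioning on baseline smoking level or OSA severity. Followed as written, that can present confounding as an effect or hide an association. For positives versus negatives, the defensible claim is narrower: the change-score and baseline-adjusted analyses rest on different assumptions, so relying on one alone is unsafe.

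The size is unknown. The range of 1.0 to 2.5 cigarettes/day rests on an assumed gap of 5, rho of 0.5 to 0.8, equal SDs and a common regression line. The false-positive rates rest further on an assumed SD of 10 and 100 patients per group. With no baseline gap there is no such bias in the change comparison. Confidence is medium, because an SAP that is not shown may already deal with this.

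**What to change.** - **Improved versus not improved, among positives.** Analyse follow-up smoking by group with baseline smoking level and baseline AHI as covariates. Report the unadjusted change alongside.
- **Positives versus negatives.** Show baseline smoking by group. Report both the change-score and the baseline-adjusted difference, and state that they rest on different assumptions when a pre-existing gap may be stable.
- **Data.** Record smoking as a quantity (for example cigarettes/day) within the detailed history already taken, and in the same unit at follow-up.
- **Wording.** Describe the results as associations, and drop the statement that improvement reduces smoking.

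**Cost.** No patients or visits are added. The smoking history must capture quantity, which the protocol does not currently specify, and there is slightly more analysis and reporting. AHI grading is already planned.

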### *Population and Sample*

A purposive sampling technique will be utilized to determine the study population. The target population is patients above the age of 18 referred for sleep study at the Jordan University Hospital and Jordan Hospital. Patients who agree to participate in this study and sign the consent form.

### *Data Collection*

Researchers will interview patients in person at their initial sleep study visit to physically examine and observe participants' faces for discoloration and take pictures for future reference with consent. Follow up at 3 weeks and 6 months will be done either in the clinic or over the phone and Email.

### *Ethical Considerations*

Informed consent will be obtained from participants with anonymity confidentiality assured. The study will be explained to patients, after which they must sign a consent form. Each will be assigned a number and the collected data will be used for analysis without reference to patients' identities. Participation does not add risk to the patients since their treatment plan will not be altered, only followed up with.
